PROSPECTIVE STUDY OF
PULMONARY COMPLICATIONS OF
HUMAN IMMUNODEFICIENCY VIRUS INFECTION

P R O T O C O L

February 25, 1991

Prospective Study of
Pulmonary Complications of Human
Immunodeficiency Virus Infection

Protocol Summary

This study seeks to provide information concerning the pulmonary diseases that occur as a result of infection with the human immunodeficiency virus (HIV). The primary objective of the study is to determine the frequency and types of lung diseases that occur in persons with HIV infection and to describe the course and outcome of these disorders. These diseases or abnormalities may be either secondary to the immunologic abnormalities caused by the virus (opportunistic processes) or the result of the HIV infection itself.

The study will be based in seven Clinical Centers (six in the United States and one in Europe) and will be a prospective, longitudinal evaluation of a cohort of seropositive persons and seronegative control subjects. Seropositive subjects will be stratified into two groups defined by the number of circulating CD-4 cells (≥ 400 per microliter, < 400 per microliter) and the presence or absence of "pre-AIDS" conditions. Evaluations of these three groups will enable identification of the lung diseases that occur at various stages of HIV disease. The "background" prevalence/incidence of various diseases and abnormalities that are related to demographic, environmental, or lifestyle factors, rather than HIV infection, will be determined by evaluation of the seronegative group.

Evaluations will be conducted at regular intervals and when predefined symptoms occur. Screening and diagnostic studies that are of proven value in detecting AIDS-associated lung diseases will be used. Tests will be performed in a uniform manner using standardized techniques among all Clinical Centers. Subjects will be followed for between 3 and 4 years (one year recruitment period and 3 year period of observation) or until death.

As a substudy, the effect of early detection of P. carinii pneumonia on subsequent morbidity and mortality will be evaluated. Seropositive subjects will be allocated at random to either "routine" (testing at 12-

month intervals) or "intensive" (testing at 3-month intervals) evaluations.

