The reports of both LIP and NIP also suggest that there are pulmonary diseases associated with HIV infection that might be due to HIV itself. Again, the natural history of these processes has not been elucidated and the implications of finding LIP and NIP for the eventual course of HIV disease have not been determined.

A prospective longitudinal evaluation of a cohort of persons with HIV disease at various stages in its evolution as described in this protocol can identify the spectrum of pulmonary disorders associated with HIV infection and describe their "natural" history. Both screening and diagnostic studies that are of proven value in the evaluation of patients who are suspected of having HIV-related pulmonary disorders will be applied in a uniform manner according to predefined criteria.

By so doing the findings will be comparable among the centers participating in the study and, thus, will provide a much broader picture of the full range of lung disorders in a variety of HIV transmission categories and geographic areas than currently exists. Designing the study cohort to include persons in the major HIV transmission categories should enable determination of differences in the relative and absolute frequencies of lung diseases in these groups.

Continued use of standardized pulmonary evaluations and careful clinical follow-up will provide a description of the patient's course after a lung disease has been diagnosed and will identify the disorders that occur subsequent to an initial pulmonary disease. Within the context of the study the utility of tests to identify second and subsequent episodes of P. carinii pneumonia will be determined.

The subjects in the cohort will be characterized by clinical features and immunologic tests that previous epidemiologic studies have shown to be predictive for the subsequent development of AIDS. Correlation of the results of these tests with pulmonary abnormalities will enable identification of variables that are associated with or predictive of specific lung disorders.

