Laboratory findings - hemoglobin, hematocrit, white blood cell count, absolute number of neutrophils, lymphocytes and monocytes, liver function tests (bilirubin, SGOT, SGPT, alkaline phosphatase, total serum proteins, albumin) erythrocyte sedimentation rate, lactate dehydrogenase
Tests of immune status - intradermal tests (tuberculin, trichophyton, candida), lymphocyte subsets (CD3, CD4, CD8)
Tests of HIV activity - P-24 antigen, beta-2 microglobulin.

Confounding variables

Coexisting nonHIV-related diseases
Immunosuppressive therapy or conditions
Multiple coexisting HIV-related diseases
Antiviral therapy
Antipneumocystis preventive therapy

Outcome variables

Presence of recurrent P. carinii pneumonia

Analysis

Analysis strategies will be similar to those used in answering Question 4.

Question 6. Are the relative frequencies of pulmonary diseases different in homosexual/bisexual men compared with intravenous drug abusers?

Groups studied

All HIV seropositive subjects

Predictive variables

HIV transmission category

Confounding variables

Place of residence (Clinical Center)
Age
Sex
Clinical and immunologic stage of HIV infection
Coexisting nonHIV-related diseases
Antiviral therapy
Preventive therapy for HIV-related processes

Outcome variables

Specific HIV-related diseases

Analysis

Categorical data analysis techniques based on minimum Chi-square methods (e.g., the CATMOD procedure in SAS) will be used to address this question. Some comparisons with the HIV negative group may also be used in this context

Precision

Half-width 95% confidence interval for the differences in prevalence of defined diseases between homosexual/bisexual and IV drug user is 4%.

Question 7. Do the relative frequencies of pulmonary diseases differ among the different Clinical Centers participating in the study?

Groups studied

All HIV seropositive subjects

Predictive variables

Clinical Center in which the subject is enrolled

Confounding variables

HIV transmission category

Age

Sex

Clinical and immunologic stage of HIV infection

Coexisting nonHIV-related diseases

Antiviral therapy

Preventive therapy for HIV-related diseases

Outcome variables

Specific HIV-related diseases

Analysis

This question will be addressed with the mathematical model used to answer Question 6.

Question 8. Are different stages of HIV infection as defined by absolute and relative numbers of CD4 cells associated with different HIV-related pulmonary diseases?

Groups studied

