Pneumocystis carinii pneumonia - Definite: Recovery of organisms on smear of lung derived specimens. Presumptive: The physician investigator must first review all available medical information and make a decision that a diagnosis of presumptive Pneumocystis carinii pneumonia is justified. First episode: The diagnosis of Pneumocystis carinii pneumonia (either definite or presumptive, as defined above) on the first such occasion. Episodes subject to first: the finding of P. carinii in any lung derived specimen, or the diagnosis of presumptive P. carinii pneumonia (as defined above) more than 2 months after completion of treatment for a previous episode and compatible clinical findings.

Tuberculosis - Pulmonary: Positive culture of lung derived specimen and an abnormality on chest x-ray or a compatible clinical picture. Extra pulmonary: Isolation of M. tuberculosis from any extra pulmonary source.

M. avium complex and other nontuberculous mycobacteria - Pulmonary: Isolation of M. avium or other nontuberculous mycobacteria from a lung-derived specimen in a patient with clinical illness who has no other pulmonary diseases identified. Extrapulmonary: Isolation of M. avium or other nontuberculous mycobacteria from an extrapulmonary source.

Cytomegalovirus Infection - Pulmonary: Demonstration of lung cell (including alveolar macrophage) infection by characteristic intranuclear and/or cytoplasmic inclusion bodies or by labelled specific DNA probes or monoclonal antibodies. Isolation of CMV from a respiratory specimen is desirable but optional for confirmation. Extrapulmonary: Demonstration of cell infection by characteristic intranuclear and/or cytoplasmic inclusion bodies. Isolation of CMV from blood.

Toxoplasmosis - Pulmonary: Histopathologic identification of T. gondii in lung tissue. Extrapulmonary: Histopathologic identification of T. gondii in extrapulmonary tissue. Diagnostic changes (2 fold in 3 weeks) in IgG titer or single IgM titer of 1:160 or higher. Of the brain: radiographic improvement after specific treatment for toxoplasmosis or recovery of organisms from brain tissue.

Pulmonary strongyloidiasis - Demonstration of larvae in any lung-derived specimen or demonstration of larvae in stool or duodenal aspirate and a clinical picture compatible with disseminated infection involving the lungs.

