- 5) Selected physicians providing primary care to a large number of HIV-infected patients in Frankfurt will be approached and invited to refer their patients for regular pulmonary work-ups in our department.

In case the number of participants recruited from PACS from these sources during the first 3 months of the study is less than required, we intend to publish the aims of this study in regional newspapers and on radio and TV inviting potential participants to join the study.

Individuals for Group C (control) will be recruited from a cohort of non-infected sexual partners of HIV patients currently studied at Frankfurt University Hospital. A special effort is made to recruit HIV seronegative IV drug abusers who are treated in the emergency room of Frankfurt University Hospital.

Appendix 5

Procedures

Pulmonary Complications of HIV Infection

Manual for Diagnostic Procedures,
Specimen Collection and Processing

PULMONARY COMPLICATIONS OF HIV INFECTION
DIAGNOSTIC SPECIMEN PROCESSING

I. Routine Studies

- A. Sputum Collection -- induced with ultrasonic nebulizer (USN)
 - 1) Stains: P. carinii, (Giemsa, silver, toluidine blue, DFA), acid fast, papanicolaou, CMV DNA probe - optional)
 - 2) Cultures: mycobacterial (viral, fungal - optional)
- B. Bronchoscopy -- Bronchoalveolar lavage -- optional
 - 1) Stains: P. carinii (Giemsa, silver, toluidine blue) acid fast, papanicolaou (CMV DNA probe - optional)
 - 2) Cultures: mycobacterial, fungal, viral

II. Diagnostic Evaluations

- A. Sputum Collection
 - 1) Spontaneous:
 - a) Stains: Gram's, acid fast
 - b) Cultures: bacterial, mycobacterial, fungal
 - 2) Induced with USN
 - a) Stains: P. carinii (Giemsa, silver, toluidine blue), acid fast, papanicolaou, CMV DNA probe, Legionella DFA or Probe, Mycoplasma Probe (e.g., all but Giemsa, Acid Fast - optional)
 - b) Cultures: mycobacterial, fungal (viral, Legionella, Mycoplasma - optional)
- B. Bronchoscopy
 - 1) Bronchoalveolar Lavage
 - a) Stains: P. carinii (Giemsa, silver, toluidine blue), acid fast, (Papanicolaou, Legionella, DFA, CMV DNA Probe, Legionella Probe, Mycoplasma Probe - optional)
 - b) Cultures: mycobacterial, fungal (viral, Legionella, Mycoplasma - optional)
 - 2) Transbronchial Biopsy
 - a) Stains: Silver, Acid Fast, Hematoxylin and Eosin
 - b) Touchprep: (Giemsa, silver, toluidine blue - optional)
 - c) Cultures: (mycobacterial, fungal - optional)
 - 3) Transbronchial Needle Aspiration
 - a) Stains: Papanicolaou, Silver, Acid Fast

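### Tests that detect CMV, herpes simplex, Legionella and Mycoplasma are optional on diagnostic sputum and lavage, so between-center differences for these agents (Question 7) may partly reflect testing practice

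*Protocol*

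**What the plan says.** The Protocol Summary states: "Tests will be performed in a uniform manner using standardized techniques among all Clinical Centers". Section 4 (Rationale) ties comparability to uniform application of screening and diagnostic studies: "By so doing the findings will be comparable among the centers participating in the study". Section 7.2 says that the evaluations follow uniform methods and refers to Appendix 5 for them.

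Appendix 5, Diagnostic Specimen Processing, part II, is less uniform:

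- **Cultures, induced sputum and BAL:** "Cultures: mycobacterial, fungal (viral, Legionella, Mycoplasma - optional").
- **Stains and probes, BAL:** "acid fast, (Papanicolaou, Legionella, DFA, CMV DNA Probe, Legionella Probe, Mycoplasma Probe - optional").
- **Stains and probes, induced sputum:** the list ends "Mycoplasma Probe (e.g., all but Giemsa, Acid Fast - optional").

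No text says who decides on an optional test, or when.

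Appendix 2 makes these infections study diagnoses. Pulmonary CMV requires "Demonstration of lung cell (including alveolar macrophage) infection by characteristic intranuclear and/or cytoplasmic inclusion bodies or by labelled specific DNA probes or monoclonal antibodies", and viral isolation serves only as confirmation. Pulmonary herpes simplex requires culture or typical cells or inclusions. Legionella and Mycoplasma require isolation or serology.

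Appendix 1 asks: "Question 7. Do the relative frequencies of pulmonary diseases differ among the different Clinical Centers participating in the study"? The population is all HIV seropositive subjects, the predictor is the Clinical Center and the outcome is specific HIV-related diseases. The listed confounders do not include whether a test was performed. CMV is also one of the four diseases named first in Question 2, and Section 9 names it among the major diseases of Question 3.

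**The concern.** A comparison of disease frequency between centers needs roughly equal detection in each. If one center regularly runs the CMV probe, Papanicolaou stain and viral culture on lavage fluid and another seldom does, the first will record more CMV even when the true frequency is the same. Entering center in the model cannot correct this, because in Question 7 center is the exposure.

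The same weakness reaches CMV elsewhere. In Question 1, under-detection lowers the pooled frequency. In Questions 2 and 3, the group without diagnosed CMV may include infected subjects who were not tested, which would distort associations with mortality and with co-infection. For Question 3 the sequence in Section 7.2.4 adds to this: bronchoscopy is called for when induced sputum yields no pathogen. A sputum positive for *P. carinii* may therefore end the search for CMV unless optional sputum tests were also run.

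**Working it through.** The protocol states no precision or power for Question 7, so there is no figure to reproduce. The check has two parts.

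**1. Are the detecting tests really optional, and what other routes remain?** Appendix 2 set against Appendix 5 and related sections:

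| Agent | Optional on diagnostic sputum and BAL | Other routes to the Appendix 2 definition |
|---|---|---|
| CMV | Papanicolaou, CMV probe | Hematoxylin-eosin on transbronchial biopsy, thoracotomy or autopsy tissue |
| Herpes simplex | Papanicolaou, viral culture | The same tissue; viral culture at thoracotomy, and at autopsy within 72 hours of death |
| Legionella | Culture, DFA, probe | Culture at thoracotomy; IFA serology |
| Mycoplasma | Culture, probe | Complement-fixation serology |

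The other routes exist, but none is assured for every evaluation. The bronchoscopy procedure words transbronchial biopsy conditionally. Thoracotomy and autopsy cover few subjects. No Legionella or Mycoplasma serology appears in the blood tests of Section 7.2.4 or in the Appendix 5 specimen list. By contrast, on the same diagnostic sputum and BAL specimens at least one *P. carinii* stain, the acid-fast stain, and mycobacterial and fungal cultures carry no optional label.

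**2. How large could the artefact be?** All rates and uptake figures below are assumptions.

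*Seropositive denominator, as in Question 7.* Section 7.1.4 gives 85 + 85 = 170 seropositives per center. After the planned 12% loss, 170 × 0.88 = 149.6, about 150. Assume the same true rate p in all seven centers, four centers that find every case, and three that find a share s. With p_i the detected rate in center i and p̄ their mean, the noncentrality is

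λ = Σ 150(p_i − p̄)² / [p̄(1 − p̄)],

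and the chance of a false center difference is P(χ²₆(λ) > 12.59), at nominal 5%.

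For p = 5% and s = 0: p̄ = 4 × 0.05 / 7 = 0.0286; λ = 150 × [4(0.0214)² + 3(0.0286)²] / (0.0286 × 0.9714) = 23.2; probability 97%.

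| True rate | s = 0 | s = 0.5 |
|---|---|---|
| 2% | 60% (λ = 9.1) | 13% (λ = 1.7) |
| 5% | 97% (λ = 23.2) | 29% (λ = 4.3) |
| 10% | >99% (λ = 47.7) | 58% (λ = 8.9) |

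*Bronchoscopy denominator.* Assume 40 bronchoscopies per center, 15% true detection (6 cases), and three centers that test and four that do not.

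- No detection without the optional tests: counts 6, 6, 6, 0, 0, 0, 0 give χ² = 25.65 on 6 df, p = 0.0003, and a pooled frequency of 18/280 = 6.4% instead of 15%.
- Half the cases found by other routes: counts 6, 6, 6, 3, 3, 3, 3 give χ² = 4.03, p = 0.67, and a pooled frequency of 30/280 = 10.7%.

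If all centers test, or none does, s = 1 in effect and the between-center artefact vanishes.

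**The case against.** The strongest reply is that the protocol never sets up the error. A reader might infer that untested subjects or centers will be counted as disease-free in Question 7. No passage says so. The nearest text, in Question 11, takes absence of disease from a lack of findings on evaluation or from the clinical course, and it applies to that question only. Appendix 1 states that it is not an exhaustive list of analytical approaches, and a statistical analysis plan could set the denominator. This stands.

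A reader might also infer that each center adopts or drops a test wholesale. Appendix 5 says only that the tests are optional, so case-by-case use fits equally well. Nor is detection zero without them, given the routes listed above. Section 10.2.6 adds central review of all fixed tissue and cytologic slides, with consensus correction. The diagnostic algorithms (Figures 2 to 7) are not visible and may require biopsy in some pathways. These points also stand, and they rule out the claim that a center omitting the optional tests has almost no way to diagnose these infections.

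Legionella and Mycoplasma are weaker examples than CMV: Table 1 does not name them as HIV-related, although Appendix 2 defines both.

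What the reply does not remove is the conflict inside the protocol. Central review cannot find organisms on slides or in cultures that were never made. An analysis plan can handle untested evaluations only if testing is coded, and the one reporting duty in the Appendix 5 specimen section covers culture media and non-standard techniques, not which optional tests are used.

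**Conclusion.** The concern holds in a limited form. The statements on uniform methods and comparable centers conflict with Appendix 5, which leaves the main detecting tests for four agents optional on the main diagnostic specimens. Question 7 compares centers without accounting for testing. Differences between centers for CMV, herpes simplex, Legionella and Mycoplasma, and CMV frequencies and associations in Questions 1 to 3, may therefore partly reflect testing practice.

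The size cannot be fixed from the document. Under the assumptions shown, the false-difference rate runs from 13% to above 99%, against a nominal 5%, and the bronchoscopy example moves from p = 0.0003 to p = 0.67 once other routes find half the cases. The document does not support saying that Question 7 will report laboratory policy as center differences. It supports saying that this can happen and that the plan as written could not tell the two apart. CMV matters most, because Questions 2 and 3 name it among their main diseases.

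**What to change.** 1. Reconcile Section 7.2 and the uniformity statements with Appendix 5, so that the protocol says one thing about which tests are common to all centers.
2. Limit the formal between-center comparison in Question 7 to diseases whose detecting tests Appendix 5 fixes at every center: *P. carinii*, mycobacteria and fungi. Pulmonary candidiasis needs a check here, because Appendix 2 defines it by histology rather than culture.
3. For CMV, herpes simplex, Legionella and Mycoplasma, code test done or not done for each evaluation. Section 8.6 already has visit records listing the tests conducted. Report the proportion tested by center and present the center results descriptively.
4. For CMV in Questions 1 to 3, keep the analysis of all seropositive subjects as the main one and add a tested-only sensitivity analysis.

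A tested-only denominator should not become the main estimate. If optional tests are ordered on suspicion, it selects by indication and inflates frequency, and it departs from the stated population of all seropositives.

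The cost is some wording and one coded item per test and evaluation. The price is the loss of a formal center comparison for the four agents, and a sensitivity analysis for CMV that may itself be biased upward.
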